## 8. SOFTWARE

All analyses will be generated using SAS Version 9.4 or higher.

## 10. APPENDIX

### 10.1. Summary of Statistical Analyses

#### Primary Efficacy Analysis:

Endpoint	Analysis Populations	Statistical Method	Supportive Analysis	Subgroup Analysis	Other Analyses
Percent change from baseline in LDL-C at week 12	ITT	MMRM	Yes, including handling of missing data	Yes	1) On-treatment estimand 2) Actual stratification factor 3) Multiple Imputations + ANCOVA 4) Pattern mixture model

### 10.2. Windows for Analysis Time Points

Below are the definitions for the visit windows programmatically imposed on measures repeatedly collected over the course of the study. These visit windows reflect the study schedule of assessments as described in the protocol. The visit windows are constructed using ranges applied to the number of days in study (study days) when the measure is collected. Day 1 is defined as the first date of double-blind study treatment administration, and is labeled as baseline for most variables. Since the protocol specifies that measurements be collected before study treatment is administered on a given day, it is appropriate that baseline include Day 1. For randomized but not treated patients, Day 1 is the day of randomization.

**Table 1a Analysis Windows Definition for Double-Blind Period – All Endpoints Except Vital Signs**

Time point	Targeted study day	Analysis window in study days
Week 4	29	15 to 42
Week 8	57	43 to 70
Week 12	85	71 to minimum of: 98 OR study day corresponding to the first open-label injection for patients entering open-label period

Study days are calculated from the day of first double-blind IMP injection, the day of first double-blind IMP injection being Day 1. For randomized but not treated patients, Day 1 is the day of randomization.

**Table 1b Analysis Windows Definition for Double-Blind Period – Vital Signs**

Time point	Targeted study day	Analysis window in study days
Week 4	29	15 to 42
Week 8	57	43 to 63
Week 10	71	64 to 77
Week 12	85	78 to minimum of: 98 OR study day corresponding to the first open-label injection for patients entering open-label period

Study days are calculated from the day of first double-blind IMP injection, the day of first double-blind IMP injection being Day 1. For randomized but not treated patients, Day 1 is the day of randomization.

**Table 2 Analysis Windows Definition for Open-Label Period**

Time point	Targeted study day	Analysis window in study days
Week 18	43	22 to 63
Week 24	85	64 to 105

Study days are calculated from the day of first open-label IMP injection. The day of first open-label IMP injection being Day 1.

### 10.3. Criteria for Potential Clinical Significant Abnormalities (PCSA)

Parameter	PCSA	Comments
Clinical Chemistry		
ALT	By distribution analysis : Enzymes activities must be expressed in ULN, not in IU/L. >3 ULN >5 ULN >10 ULN >20 ULN	Concept paper on DILI – FDA draft Guidance Oct 2007. Internal DILI WG Oct 2008. Categories are cumulative. First row is mandatory. Rows following one mentioning zero can be deleted.
AST	By distribution analysis : Enzymes activities must be expressed in ULN, not in IU/L. >3 ULN >5 ULN >10 ULN >20 ULN	Concept paper on DILI – FDA draft Guidance Oct 2007. Internal DILI WG Oct 2008. Categories are cumulative. First row is mandatory. Rows following one mentioning zero can be deleted.
Alkaline Phosphatase	>1.5 ULN	Enzymes activities must be expressed in ULN, not in IU/L. Concept paper on DILI – FDA draft Guidance Oct 2007. Internal DILI WG Oct 2008.
Total Bilirubin	>1.5 ULN >2 ULN	Must be expressed in ULN, not in $\mu\text{mol}/\text{L}$ or $\text{mg}/\text{L}$ . Categories are cumulative. Concept paper on DILI – FDA draft Guidance Oct 2007. Internal DILI WG Oct 2008.
Conjugated Bilirubin	>35% Total Bilirubin and TBILI>1.5 ULN	Conjugated bilirubin dosed on a case-by-case basis.
ALT and Total Bilirubin	ALT>3 ULN and TBILI>2 ULN	Concept paper on DILI – FDA draft Guidance Oct 2007. Internal DILI WG Oct 2008. To be counted within a same treatment phase, whatever the interval between measurement.
CPK	>3 ULN >10 ULN	FDA Feb 2005. Am J Cardiol April 2006. Categories are cumulative. First row is mandatory. Rows following one mentioning zero can be deleted.

Parameter	PCSA	Comments
Creatinine	$\geq 150 \text{ } \mu\text{mol/L}$ (Adults) $\geq 30\%$ change from baseline $\geq 100\%$ change from baseline	Benichou C., 1994.
CLcr (mL/min) (Estimated creatinine clearance based on the Cokcroft-Gault equation)	$\geq 15 - < 30$ (severe decrease in GFR) $\geq 30 - < 60$ (moderate decrease in GFR) $\geq 60 - < 90$ (mild decrease in GFR) $\geq 90$ (normal GFR)	Use is optional. FDA draft Guidance 2010 Pharmacokinetics in patients with impaired renal function-study design, data analysis, and impact on dosing and labeling
eGFR (mL/min/1.73m  ) (Estimate of GFR based on an MDRD equation)	$\geq 15 - < 30$ (severe decrease in GFR) $\geq 30 - < 60$ (moderate decrease in GFR) $\geq 60 - < 90$ (mild decrease in GFR) $\geq 90$ (normal GFR)	Use is optional. FDA draft Guidance 2010 Pharmacokinetics in patients with impaired renal function-study design, data analysis, and impact on dosing and labeling
Uric Acid		Harrison- Principles of internal Medicine 17 th Ed., 2008.
Hyperuricemia	$> 408 \text{ } \mu\text{mol/L}$	
Hypouricemia	$< 120 \text{ } \mu\text{mol/L}$	
Blood Urea Nitrogen	$\geq 17 \text{ mmol/L}$	
Chloride	$< 80 \text{ mmol/L}$ $> 115 \text{ mmol/L}$	
Sodium	$\leq 129 \text{ mmol/L}$ $\geq 160 \text{ mmol/L}$	
Potassium	$< 3 \text{ mmol/L}$ $\geq 5.5 \text{ mmol/L}$	FDA Feb 2005.
Lipasemia	$\geq 3 \text{ ULN}$	
Amylasemia	$\geq 3 \text{ ULN}$	
Glucose		
Hypoglycaemia	$\leq 3.9 \text{ mmol/L}$ and $< \text{LLN}$	ADA May 2005.
Hyperglycaemia	$\geq 11.1 \text{ mmol/L}$ (unfasted); $\geq 7 \text{ mmol/L}$ (fasted)	ADA Jan 2008.

Parameter	PCSA	Comments
HbA1c	>8%	
Albumin	≤25 g/L	
CRP	>2 ULN or >10 mg/L (if ULN not provided)	FDA Sept 2005.
Hematology		
WBC	<3.0 Giga/L (Non-Black); Increase in WBC: not relevant. <2.0 Giga/L (Black) ≥16.0 Giga/L	To be interpreted only if no differential count available.
Lymphocytes	>4.0 Giga/L	
Neutrophils	<1.5 Giga/L (Non-Black); <1.0 Giga/L (Black)	International Consensus meeting on drug-induced blood cytopenias, 1991. FDA criteria.
Monocytes	>0.7 Giga/L	
Basophils	>0.1 Giga/L	
Eosinophils	>0.5 Giga/L or >ULN (if ULN ≥ 0.5 Giga/L)	Harrison- Principles of internal Medicine 17 th Ed., 2008.
Hemoglobin	≤115 g/L (Male); ≤95 g/L (Female) ≥185 g/L (Male); ≥165 g/L (Female)	Criteria based upon decrease from baseline are more relevant than based on absolute value. Other categories for decrease from baseline can be used (≥30 g/L, ≥40 g/L, ≥50 g/L).
Decrease from Baseline ≥20 g/L		
Hematocrit	≤0.37 v/v (Male) ; ≤0.32 v/v (Female) ≥0.55 v/v (Male) ; ≥0.5 v/v (Female)	
RBC	≥6 Tera/L	Unless specifically required for particular drug development, the analysis is redundant with that of Hb. Otherwise, consider FDA criteria.
Platelets	<100 Giga/L ≥700 Giga/L	International Consensus meeting on drug-induced blood cytopenias, 1991.

Parameter	PCSA	Comments
Urinalysis		
pH	$\leq 4.6$ $\geq 8$	
Vital signs		
HR	$\leq 50$ bpm and decrease from baseline $\geq 20$ bpm $\geq 120$ bpm and increase from baseline $\geq 20$ bpm	To be applied for all positions (including missing) except STANDING.
SBP	$\leq 95$ mmHg and decrease from baseline $\geq 20$ mmHg $\geq 160$ mmHg and increase from baseline $\geq 20$ mmHg	To be applied for all positions (including missing) except STANDING.
DBP	$\leq 45$ mmHg and decrease from baseline $\geq 10$ mmHg $\geq 110$ mmHg and increase from baseline $\geq 10$ mmHg	To be applied for all positions (including missing) except STANDING.
Orthostatic Hypotension		
Orthostatic SDB		
Orthostatic DBP	$\leq -20$ mmHg $\leq -10$ mmHg	
Weight	$\geq 5\%$ increase from baseline $\geq 5\%$ decrease from baseline	FDA Feb 2007.
ECG		
		Ref.: CPMP 1997 guideline.
HR	$\leq 50$ bpm and decrease from baseline $\geq 20$ bpm $\geq 120$ bpm and increase from baseline $\geq 20$ bpm	
PR	$\geq 220$ ms and increase from baseline $\geq 20$ ms	
QRS	$\geq 120$ ms	

Parameter	PCSA	Comments
QTc	Absolute values (ms)	To be applied to any kind of QT correction formula.
Borderline		
Prolonged*	Borderline: 431-450 ms (Male); 451-470 ms (Female)	
Additional	Prolonged: >450 ms (Male); >470 ms (Female) ≥500 ms	*QTc prolonged and $\Delta$ QTc>60 ms are the PCSA to be identified in individual subjects/patients listings.
	Increase from baseline	
	Borderline: Increase from baseline 30-60 ms	
	Prolonged: Increase from baseline >60 ms	

## 10.4. EQ-5D Patient Questionnaire and Algorithme

By placing a tick in one box in each group below, please indicate which statements best describe your own health state today.

### **Mobility**

I have no problems in walking about

I have some problems in walking about

I am confined to bed

### **Self-Care**

I have no problems with self-care

I have some problems washing or dressing myself

I am unable to wash or dress myself

### **Usual Activities** (e.g. work, study, housework, family or leisure activities)

I have no problems with performing my usual activities

I have some problems with performing my usual activities

I am unable to perform my usual activities

### **Pain/Discomfort**

I have no pain or discomfort

I have moderate pain or discomfort

I have extreme pain or discomfort

### **Anxiety/Depression**

I am not anxious or depressed

I am moderately anxious or depressed

I am extremely anxious or depressed

## 10.5. List of MedDRA terms for CMQs

**Table 3** Selected PTs from SMQ “Optic nerve disorders” including in the CMQ for neurologic events

MedDRA Term Label
Benign neoplasm of optic nerve
Optic atrophy
Optic discs blurred
Optic nerve disorder
Optic nerve injury
Optic nerve neoplasm
Optic nerve operation
Optic neuropathy
Papillitis
Pseudopapilloedema
Subacute myelo-opticoneuropathy
Toxic optic neuropathy
Visual evoked potentials abnormal
Amaurosis fugax
Blindness
Blindness unilateral
Colour blindness acquired
Colour vision tests abnormal
Cranial nerve injury
Delayed myelination
Fundoscopy abnormal
Hemianopia
Hemianopia heteronymous
Hemianopia homonymous
Loss of visual contrast sensitivity
Neuro-ophthalmological test abnormal
Night blindness
Ophthalmological examination abnormal
Optic pathway injury
Optical coherence tomography abnormal
Quadrantanopia
Visual acuity reduced
Visual acuity reduced transiently
Visual acuity tests abnormal
Visual field defect
Visual field tests abnormal
Visual impairment
Visual pathway disorder

**Table 4 CMQ “Neurocognitive disorders – FDA’s recommendation”**

MedDRA level	MedDRA Term Label
PTCD	Amnesia
PTCD	Amnestic disorder
PTCD	Anterograde Amnesia
PTCD	Behavioural and Psychiatric Symptoms of Dementia
PTCD	Change in sustained attention
LLTCD	Cognitive Deterioration
PTCD	Cognitive Disorder
LLTCD	Confusion
LLTCD	Confusion Aggravated
PTCD	Confusional State
PTCD	Delirium
PTCD	Dementia
PTCD	Dementia Alzheimer's type
LLTCD	Dementia Nos
LLTCD	Dementia Nos Aggravated
LLTCD	Dementia of the Alzheimer's type NOS
PTCD	Dementia with Lewy Bodies
PTCD	Disorientation
PTCD	Disturbance in attention
PTCD	Executive dysfunction
PTCD	Frontotemporal Dementia
LLTCD	Global Amnesia
PTCD	Illogical Thinking
PTCD	Impaired reasoning
PTCD	Incoherent
PTCD	Judgement impaired
PTCD	Memory Impairment
PTCD	Mental Impairment
LLTCD	Mental Impairment Nos
LLTCD	Mental State Abnormal Aggravated
PTCD	Mental Status Changes
PTCD	Mini Mental Status Examination Abnormal
PTCD	Presenile Dementia
PTCD	Retrograde Amnesia
PTCD	Senile Dementia
LLTCD	Senile Dementia Nos
LLTCD	Short-term Memory Loss
PTCD	Thinking Abnormal
LLTCD	Thinking Slowed
PTCD	Transient Global Amnesia

MedDRA level	MedDRA Term Label
PTCD	Vascular Dementia

## 10.6. Detailed Description of the Multiple Imputation Procedure

The following is a detailed description of the multiple imputation procedure which will be used for sensitivity analysis of primary efficacy endpoint as well as the analysis of the secondary efficacy endpoints.

In general, the missing pattern is anticipated to be not monotone, a two-step approach will be used:

- Step 1: the MCMC method will be used in conjunction with the IMPUTE=MONOTONE option to create an imputed data set with a monotone missing pattern.
- Step 2: Using the monotone data set from step 1, missing data will be imputed using the regression method.

The imputation model for step 1 will include the treatment group and the values of the analyzed parameter at baseline and planned time-points up to week 12.

The imputation model for step 2 will include the same variables as in step 1 with the following additional variables:

- the randomization strata (apheresis treatment status strata);
- age, BMI, and gender (age and BMI included as continuous variables).

Non-continuous variables included in the imputer's model (i.e., treatment group, randomization strata and gender) are not expected to be missing.

In addition, for continuous efficacy variables anticipated to have a non-normal distribution (i.e. TG and Lp(a)), data will be log-transformed before imputation process and then back-transformed to create the imputed data sets using the TRANSFORM statement of SAS MI procedure.

For variables other than those continuous efficacy variables anticipated to have a non-normal distribution (i.e. TG and Lp(a)), for each simulation leading to negative imputed value, another value will be redrawn using MINIMUM option of MI SAS procedure.

The number of imputations (100) will be informally verified by replicating sets of 100 imputations and checking whether the combined results are stable. If not stable, the number of imputations will be increased and informally checked as above, and thus continued until stable estimates are obtained.

## 10.7. Detailed Description of Pattern Mixture Model

As a sensitivity analysis of the primary efficacy endpoint (i.e. percent change from baseline to Week 12 in LDL-C), a pattern-mixture model approach will be used, with a different imputation strategy applied for missing LDL-C values during the on-treatment period (i.e. within the time period from the first double-blind IMP injection up to the day of the last double-blind injection +21 days or to the day before the first open-label injection, whichever comes first) and missing LDL-C values after treatment discontinuation (i.e. after the day of last injection +21 days) based on the following assumptions:

- Patients within 21 days of their last IMP injection would continue to show benefit from treatment similar to that observed at the scheduled time point. Therefore, LDL-C values missing during the on-treatment period will be considered “Missing At Random” and imputed using a model estimated using all samples collected on treatment.
- Patients who stopped taking their study treatment no longer benefited from it in the future, and thus tended to have LDL-C values returning to baseline. Thus LDL-C values missing after treatment discontinuation will be imputed based on patient’s own baseline value.

[figure not shown]
The assumptions for this approach are based on the following considerations:

- Missing values during the on-treatment period are mostly consecutive to:
  - Visits performed outside of the pre-specified time-window
  - No blood sample available although visit was done
  - LDL-C not measurable due to technical reasons

[figure not shown]
In addition, these missing data are often intermittent, i.e. followed by LDL-C values collected at subsequent visits. It is therefore considered reasonable to assume that these missing data were “At Random”.

Phase 2 studies DFI11565 and R727-CL-1003 included a prospective assessment of calculated LDL-C during the follow-up period after a 12-week treatment period. These studies showed that after treatment discontinuation, the average calculated LDL-C returned to baseline level within 4 weeks after ceasing Praluent treatment (see [Figure 2](#) and [Figure 3](#)).

**Figure 2 - Study DFI11565: calculated LDL-C mean (+/- SE) percent change from baseline**

**Figure 3 - Study R-727-CL-1003: calculated LDL-C mean (+/- SE) percent change from baseline**

Missing LDL-C values will be imputed 100 times to generate 100 complete data sets. The percent change from baseline to Week 12 will be derived from observed and imputed LDL-C at this time point. The completed data sets will be analyzed using an analysis of covariance (ANCOVA) model with treatment group and randomization strata as fixed effects, and the baseline LDL-C value as continuous covariate. The results from the 100 analyses will be combined using Rubin's formulae. If necessary, the number of imputations (100) will be increased until stable estimates are obtained.

### **Imputation of missing data during the on-treatment period**

Missing LDL-C values during the on-treatment period will be imputed from other on-treatment measurements assuming Missing At Random, using SAS® MI procedure.

Only LDL-C values collected during the on-treatment period will be included in the imputation model. This way, missing LDL-C values during the on-treatment period will be imputed based solely on observed on-treatment LDL-C values.

The imputation model will include the treatment arm, baseline LDL-C value, and all LDL-C values at pre-specified visits. Since the pattern of missing data will necessarily be non-monotone, a Monte-Carlo Markov Chain (MCMC) method will be used. A minimum value of 0 will be specified in order to avoid negative imputed LDL-C values.

A sample SAS code is provided below:

```
proc mi data=DATAIN out=DATAOUT nimpute=100 minimum=0;  
  mcmc impute=monotone;  
  var ARM LDL_BASE LDL_W4 LDL_W8 LDL_W12;  
run;
```

As stated above, the input dataset DATAIN will include only LDL-C values collected during the on-treatment period. Any LDL-C values collected during the post-treatment period will be excluded from the input dataset. In practice, the MI procedure will generate imputed values for all missing values (whether on-treatment or post-treatment), but only imputed values during the on-treatment period will be kept in the final datasets that will be analyzed using ANCOVA. Imputed values during the post-treatment period will be discarded and replaced by imputed values described in the next paragraph.

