### ***Pattern mixture model***

The MMRM model relies on the “missing-at-random” (MAR) assumption. Because the possibility for a not-missing-at-random (NMAR) missingness mechanism can never be excluded, sensitivity analysis to explore the impact of non-ignorable missingness on the primary efficacy analysis will be conducted using the pattern mixture model approach as described below (see [Appendix 10.7](#) for more details).

In the pattern-mixture model approach, different imputation strategies will be applied to LDL-C values missing during the double-blind on-treatment period (i.e. within the time period from the first double-blind study treatment injection up to the day of last double-blind injection +21 days or day of the first open-label injection whichever comes first) versus LDL C values missing after treatment discontinuation (i.e. after the day of last double-blind injection +21 days) based on the following assumptions:

- Patients within 21 days of their last double-blind IMP injection would continue to show benefit from treatment similar to that observed at the scheduled time point. Therefore, LDL-C values missing during the on-treatment period (e.g., samples obtained out-side the specified window, no blood sample available although visit was performed, etc.) should be considered “Missing At Random” and imputed based on other on-treatment measurements.
- Patients who stopped taking their study treatment no longer benefited from it after discontinuation, and thus tended to have LDL-C values returning to baseline. Therefore, LDL-C values missing after treatment discontinuation should be imputed based on patient’s own baseline value.

Missing data from the randomized population will be imputed 100 times to generate 100 complete data sets, using the approach described above. The 100 completed datasets of observed and imputed LDL-C data will be used for primary efficacy analyses.

The 100 complete datasets of observed and imputed LDL-C data at week 12 will be analyzed using an ANCOVA model with treatment group and randomization strata as fixed effect, and the baseline LDL C value as continuous covariate. The MIANALYZE SAS procedure will be used to generate valid statistical inferences by combining results from the 100 analyses using Rubin’s formulae (4).

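### The on-treatment half of the SAP 10.7 pattern-mixture analysis does not work as written: its code never imputes a missing Week 12 value, and the first open-label injection day belongs to neither imputation period

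*SAP*

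**What the plan says.** SAP 10.7 divides missing LDL-C values into two classes. The on-treatment period runs "up to the day of the last double-blind injection +21 days or to the day before the first open-label injection, whichever comes first"; the other class is "missing LDL-C values after treatment discontinuation (i.e. after the day of last injection +21 days". On-treatment gaps are treated as missing at random and imputed with PROC MI. Post-treatment gaps are drawn around the patient's own baseline.

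For the on-treatment class, 10.7 shows a single sample call using "mcmc impute=monotone", with variables in the order arm, baseline, Week 4, Week 8, Week 12. Only on-treatment values enter the input data set. The text says of this call: "In practice, the MI procedure will generate imputed values for all missing values (whether on-treatment or post-treatment". It also promises that "Missing LDL-C values will be imputed 100 times to generate 100 complete data sets", which are then analysed by ANCOVA at Week 12.

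Three other places bear on this:

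- SAP 10.6 uses the same option as the first of two steps, only to make the missing pattern monotone. Its second step is: "Using the monotone data set from step 1, missing data will be imputed using the regression method". Section 10.7 neither repeats that step nor refers to 10.6.
- SAP 5.6.1.2 describes the same pattern-mixture analysis, but its on-treatment period runs "up to the day of last double-blind injection +21 days or day of the first open-label injection whichever comes first".
- SAP Table 1a closes the Week 12 window at the earlier of Day 98 and the "study day corresponding to the first open-label injection for patients entering open-label period".

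**The concern.** Protocol 10.4.3.1 names the pattern-mixture model as the check on the missing-at-random assumption, and Week 12 is the only time point its ANCOVA analyses. Two faults meet there.

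First, a missing final variable never breaks a monotone pattern, so the call shown leaves a missing Week 12 value missing. The on-treatment half then contributes no imputed value to the analysed endpoint. Patients with such a gap drop out of the ANCOVA, and the data sets are not complete.

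Second, the two period definitions leave a hole at the Week 12 visit. Read literally, a Day 85 sample is not on-treatment and so is kept out of the imputation input, and a value missing that day has no rule in 10.7. Repairing only the code would leave a Week 12 imputation model without the Day 85 samples.

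In either case a programmer must choose an unstated repair, in an analysis whose purpose is to be prespecified.

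**Working it through.** The plan states no figure on this point, so there is none to reproduce. The check has three parts.

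**1. What the single call fills.** Rule, consistent with SAP 10.6: a missing value is filled only if a later variable in the list is observed. The four Week 4 / Week 8 / Week 12 patterns with Week 12 missing (1 = present, 0 = missing) become:

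| Before | After |
|---|---|
| 1, 1, 0 | 1, 1, 0 |
| 1, 0, 0 | 1, 0, 0 |
| 0, 1, 0 | 1, 1, 0 |
| 0, 0, 0 | 0, 0, 0 |

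Week 12 is filled in 0 of 4. With independent 5% missingness at each visit (an illustration), the share of gaps filled is 1 − 0.05² = 99.75% at Week 4, 95% at Week 8 and 0% at Week 12. Full MCMC imputation, or the second step of 10.6, fills all four.

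**2. Calendar.** Inputs: last double-blind injection Day 71 and first open-label injection Day 85 (Protocol synopsis and 5.1); samples taken before dosing (Protocol 8.1.1, footnote 6).

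- On-treatment end, SAP 10.7: min(71 + 21, 85 − 1) = Day 84.
- On-treatment end, SAP 5.6.1.2: min(71 + 21, 85) = Day 85.
- Post-treatment start, SAP 10.7: 71 + 22 = Day 93.
- Unassigned under 10.7: Days 85 to 92. For a patient entering open-label on Day 85, the Week 12 window is Days 71 to 85, so the day that matters is Day 85.

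Varying the last dose over Days 68 to 74 and the first open-label dose over Days 82 to 88, the open-label injection day is unassigned in all nine combinations checked. It is not unassigned when open-label starts more than 21 days after the last double-blind dose (for example, Day 63 then Day 85), because the day is then post-treatment. Under the 5.6.1.2 boundary, no Week 12 window day is unassigned in any case checked.

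**3. Size.** Inputs: N = 74, 5% non-evaluable allowance, SD 35 (SAP 2.2).

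- Upper bound on patients affected by the code fault: 74 × 0.05 = 3.7. The documents do not split this between on- and post-treatment. At on-treatment shares of 25%, 50% and 75% it is 0.9, 1.9 and 2.8.
- Visit 5 can supply a Week 12 value if it falls on Day 71 or later. If it is attended and spread evenly over Day 71 ± 5 (assumption), 6 of 11 days qualify, and 3.7 × (1 − 6/11) = 1.7.
- SE of the treatment difference = 35 × √(1/(2N/3) + 1/(N/3)). N = 74 gives 8.63; N = 74 − 3.7 = 70.3 gives 8.86; the ratio is 1.026.
- Effect of the boundary on the imputation input, for patients starting open-label at Visit 6: if the value nearest the target day is selected before the on-treatment filter, none has a Week 12 value in the input. If the filter comes first, about 74 × 6/11 = 40 of 74 do, all from Visit 5. The SAP does not state the order.

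**The case against.** The strongest reply is that the code is labelled a sample, while the prose asks for missing-at-random imputation and complete data sets, and 10.6 says its two-step procedure serves sensitivity analyses of the primary endpoint. A careful programmer would notice the empty Week 12 cells. That is fair as a prediction, but 10.7 never cites 10.6, supplies no second step, and describes the call's output as if it were complete. Prose and code contradict each other.

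On the boundary, 5.6.1.2 does place the open-label injection day on-treatment, and the 10.7 rationale (benefit persists within 21 days of the last injection) points the same way. This shows which phrase is out of line; it does not remove the conflict. It is also right that only one day of the eight-day gap lies in the Week 12 window, and that patients who never enter open-label, or enter more than 21 days after their last dose, have no gap.

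The sizes are soft. Protocol 8.1.1, footnote 9, gives ±3 days off apheresis and +1 day on apheresis. Off apheresis an even spread gives 4/7 instead of 6/11: about 42 patients instead of 40, and 1.6 instead of 1.7. Counting apheresis patients, all at Day 71 or later, lowers the second figure further. The 2.6% compares against no missing data at all, so it overstates the loss relative to correct imputation; losing 1.7 patients gives an SE of about 8.73, or +1.2%. If no on-treatment Week 12 value is missing, the code fault changes no result.

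Finally, the separate multiple-imputation ANCOVA already imputes Week 12 under missing at random, and the return-to-baseline draw, which departs from that assumption, is sound. This limits the consequence but does not make 10.7 executable.

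**Conclusion.** Both faults hold; SAP 10.7 is wrong as written. The call shown imputes no missing Week 12 value, contrary to the text around it. On the planned schedule, the Week 12 target day falls in neither imputation period, contrary to 5.6.1.2 and Table 1a.

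The numerical effect is small: at most 3.7 of 74 patients and a 2.6% larger standard error, assuming that the whole 5% allowance is on-treatment Week 12 missingness. The boundary finding assumes open-label starts within 21 days of the last double-blind injection; the planned interval is 14 days. The primary MMRM, observed Week 12 values in the ANCOVA, and the return-to-baseline draw are not affected. The change should be made because the protocol's named robustness check cannot otherwise be run as specified.

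**What to change.** In SAP 10.7:

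1. Change the MCMC option to `impute=full`, or add a second monotone-regression step as in 10.6. Keep the imputation variables that 10.7 already lists.
2. End the on-treatment period on the day of the first open-label injection, as in 5.6.1.2, and state that samples taken before dosing that day count as on-treatment.

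The second change puts on-schedule Day 85 values into the imputation input whichever order selection and filtering take. The cost is one code option (or one added step) and one phrase in an appendix, made before database lock. No further data are needed.
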